5. SELECTION OF RESEARCH PARTICIPANTS

5.1. Inclusion Criteria

- Over 18 years of age
- Scheduled for non-urgent (>24h) cardiac surgery under CPB
- For women of childbearing age not using effective contraception: negative beta-HCG test
- Having provided written informed consent
- Covered by a social security scheme

5.2. Non-Inclusion Criteria

- Pregnant or breastfeeding women
- Patient under guardianship, curatorship, or judicial protection, or unable to provide consent
- Known allergy or intolerance to naloxegol or any of its excipients or other opioid antagonists
- Severe hepatic impairment (Child-Pugh Class C), history of cirrhosis
- Moderate or severe renal impairment (GFR <60 mL/min by MDRD)
- Known or suspected acute gastrointestinal obstruction
- Conditions likely to alter gastrointestinal wall integrity (severe peptic ulcer, Crohn's disease, diverticulitis, infiltrating tumors of the GI tract or peritoneal metastases)
- History of digestive arteritis (intestinal ischemia or sub-ischemia)
- Cancer with increased risk of gastroduodenal perforation

- Clinically significant blood-brain barrier alteration (primary brain tumor, brain metastases, active multiple sclerosis, advanced Alzheimer's disease, etc.)
- Concomitant use of strong CYP3A4 inhibitors (clarithromycin, ketoconazole, itraconazole, telithromycin; protease inhibitors: ritonavir, indinavir, saquinavir; grapefruit juice in large quantities)
- Concomitant use of methadone
- Patients regularly taking laxatives
- Patients unable to swallow a whole tablet with a small amount of water
- Patients already included or about to be included in another drug research protocol

5.3. Recruitment Methods

All patients admitted for cardiac surgery under CPB and meeting eligibility criteria will be offered participation in the study. They will be informed at the cardiology consultation before the procedure. Consent will be obtained after ensuring good understanding of the information provided.

6. RESEARCH METHODOLOGY

6.1. Study Type

Prospective, comparative, controlled, randomized, double-blind interventional study (naloxegol tablet or placebo administered by a registered nurse outside the protocol). Physicians, the nurse assessing the primary endpoint, and patients will be blinded to group allocation.

The study compares a group receiving a naloxegol 12.5mg tablet two hours before surgery and 25mg every 24h postoperatively until bowel transit recovery (maximum 5 days) against a control group receiving placebo under the same conditions.

6.2. Study Conduct

6.2.1. In the Cardiology/Cardiac Surgery Ward:

a) Inclusion: Patients will be informed of the protocol by an investigator physician during the cardiology consultation. Clear and transparent information will be provided orally and in writing. Inclusion and non-inclusion criteria will be verified. Informed consent will be obtained after a reflection period deemed sufficient by the patient.

b) Randomization: Patients will be randomized the day before surgery (1:1) into two groups:

- Naloxegol Group: Interventional arm receiving the experimental treatment 'naloxegol'
- Placebo Group: Comparison arm receiving an inert tablet

Randomization will be performed electronically via the eCRF by a nurse 'outside the protocol' who will administer the treatment according to the randomization group.

6.2.2. In the Operating Room:

Standard management of patients for anesthesia and cardiac surgery.

6.2.3. In the ICU and CCU:

- Standard patient management
- Naloxegol Group: administration of a naloxegol 25mg tablet at 24h postoperatively, then every 24h until bowel transit recovery, maximum 5 days
- Placebo Group: administration of an inert tablet at 24h postoperatively, then every 24h until bowel transit recovery, maximum 5 days
- At Day 2 in absence of bowel transit: administration of macrogol until transit recovery
- At Day 4 in absence of bowel transit: administration of sodium picosulfate (Citrifleet)

6.2.4. In the Ward and at Home:

Collection of patient vital status and possible adverse events daily during hospitalization, then at 1 month by telephone call.

6.5. Study Duration

- Planned inclusion duration: 24 months
- Individual patient participation duration: approximately 1 month
- Total study duration: approximately 25 months

6.7. Measures to Reduce or Avoid Bias

6.7.1. Patient Selection:

To avoid selection bias, this study will be proposed to all eligible patients seen at the cardiology consultation.

6.7.2. Randomization:

The treatment number will be revealed via the randomization website to the designated healthcare professional (nurse) for treatment administration. The cardiologist and nurse caring for the patient, who are the sole evaluators, will not know the randomization group, avoiding evaluation bias.

6.7.3. Blinding Procedures:

Pre-randomization will be performed by the sponsor, associating a treatment number (3 digits) with a treatment ('Naloxegol' or 'Placebo'). These numbers will appear on the treatment boxes. Each included patient will receive the treatment provided in the sequential pre-randomization order.

6.8. Stopping Rules for Individual Participants

Any subject included in the study may withdraw consent at any time for any reason without explanation and without affecting the care provided. Early death without bowel transit recovery (absence of primary endpoint) will lead to exclusion from analysis (mITT). These patients will be replaced to avoid loss of statistical power.

7. TREATMENTS ADMINISTERED TO RESEARCH PARTICIPANTS

7.1. Investigational Medicinal Product

| | |
|-----------------------|---|
| Trade Name | MOVENTIG® 12.5mg and 25mg film-coated tablets |
| INN | Naloxegol |
| Manufacturer | Piramal Healthcare UK Limited, Morpeth, United Kingdom |
| MAH | Kyowa Kirin Holdings B.V., Hoofddorp, Netherlands. EU centralized MA: December 8, 2014 |
| Dosing Regimen | 12.5mg tablet 2 hours before surgery, then 25mg every 24h after surgery until bowel transit recovery (max 5 days) |
| Placebo | Inert tablet (Arrow). Round white 300mg tablet. Administered under the same conditions as the active treatment. |

7.5. Permitted and Prohibited Concomitant Medications

Concomitant use of naloxegol with strong CYP3A4 inhibitors is contraindicated. Concomitant use with diltiazem or verapamil is not recommended as these increase naloxegol plasma concentration. The following are permitted per standard practice for transit delay management:

- At Day 2 in absence of transit: macrogol administration until transit recovery
- At Day 4 in absence of transit: sodium picosulfate (Citrafleet®)

8. SAFETY EVALUATION

8.1. Definitions

Adverse Event (AE): Any harmful manifestation occurring in a research participant, whether or not related to the research or product.

Serious Adverse Event (SAE): Any AE that causes death, threatens the life of the participant, requires hospitalization or prolongation of hospitalization, causes significant or lasting disability, or results in a congenital abnormality.

Unexpected Serious Adverse Reaction (SUSAR): Any serious adverse effect whose nature, severity, frequency, or evolution does not correspond to reference safety information.

8.4. Protocol-Specific SAEs Requiring Immediate Notification

- Severe symptomatic dehydration (liquid stools >5 times/24h requiring fluid resuscitation >1L)
- Gastrointestinal perforation
- Ogilvie syndrome
- Mesenteric ischemia
- Any severe hemodynamic change not explained by another cause requiring catecholamine support
- Any fatal adverse event, regardless of cause

8.4.2. SAEs Not Requiring Immediate Notification

SAEs related to cardiac surgery (bleeding, shock, myocardial infarction, ventricular arrhythmia, pneumothorax, reoperation) or intensive care (infection, organ failure) will not be considered related to research conduct.

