3.2. Secondary Objectives

- Evaluate the effect of naloxegol on digestive complications
- Evaluate the effect of naloxegol on respiratory complications
- Evaluate the rate of infectious complications
- Verify the maintenance of normal analgesia
- Compare total hospitalization durations
- Compare lengths of stay in intensive care unit and continuous care unit (CCU)

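### Section 8.4.2 is headed as an exemption from immediate notification, but its sentence fixes causality by event category and states no precedence against Section 8.4

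*Combined protocol and SAP*

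**What the plan says.** Section 8.4.2 carries the heading "SAEs Not Requiring Immediate Notification". Its only sentence covers "SAEs related to cardiac surgery (bleeding, shock, myocardial infarction, ventricular arrhythmia, pneumothorax, reoperation") and then continues "or intensive care (infection, organ failure) will not be considered related to research conduct". The sentence itself does not mention notification.

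Section 8.4 lists the events that must be notified at once. Two items matter most here: "Any severe hemodynamic change not explained by another cause requiring catecholamine support" and "Any fatal adverse event, regardless of cause". Gastrointestinal perforation, mesenteric ischaemia, Ogilvie syndrome and severe dehydration are also on that list.

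Section 8.1 defines an adverse event "whether or not related to the research or product", and defines a SUSAR as a serious adverse effect that departs from the reference safety information. Section 6.2.4 collects vital status and adverse events daily in hospital and by telephone at one month. Section 3.2 includes the objective "Evaluate the rate of infectious complications".

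**The concern.** When an event must be reported and whether the drug may have caused it are separate questions. A sponsor may reasonably exempt expected postoperative events from immediate notification. Section 8.4.2 goes further and answers the causality question in advance, by event type.

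A SUSAR begins with a suspicion of causality in an individual patient. If an event is unrelated by rule, that suspicion cannot be recorded and the event cannot enter the SUSAR route, whatever its timing or features. The listed events are ones the protocol itself attributes to cardiac surgery or intensive care, and Section 2.4 makes the whole population cardiac surgery patients on bypass. The surgical label is thus available for nearly every such event.

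The second issue is overlap. Some events meet the terms of both 8.4 and 8.4.2, and the text does not say which governs.

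**Working it through.** The plan gives no figure on this point, so the main check is a comparison of sections.

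**1. Heading against sentence.** The heading of 8.4.2 concerns timing and the sentence concerns relatedness. Neither implies the other: an event can be exempt from immediate notification and still be judged related later.

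**2. Scope.** Surgical classes: bleeding, shock, myocardial infarction, ventricular arrhythmia, pneumothorax, reoperation (6). Intensive-care classes: infection, organ failure (2). Total 6 + 2 = 8. Only ventricular arrhythmia is named, not arrhythmia in general.

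**3. Which classes are visible elsewhere in the plan (Section 4.2).**
- Infection: septicaemia, sternal infection and pneumonia are secondary endpoints, and Section 9.1 compares categorical variables between the randomised groups. An imbalance would show whatever causality was assigned.
- Reoperation: captured only in part, as return to theatre for a sternal wound.
- Organ failure: not an endpoint as such. The ventilation and reintubation endpoints reflect its respiratory part only.
- Bleeding, shock, myocardial infarction, ventricular arrhythmia, pneumothorax: not listed endpoints.

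Section 9 as supplied describes no tabulation of serious adverse events by arm. The only analysis population it shows (Section 9.7) leaves out patients who died early without transit recovery.

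**4. Overlap with 8.4.**
- Deaths: a fatal infarction, shock, infection or organ failure meets the fatal-event item in 8.4 and also falls under the not-immediate heading of 8.4.2. This is the clearest overlap.
- Haemodynamic change: 8.4 is limited to changes without another explanation, and 8.4.2 to events attributed to surgery or intensive care. The two can be complementary, but only if someone decides the cause in each case. Neither section says who does so, and 8.4.2 names shock as surgical.

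**5. Could a comparison by arm replace individual assessment?** This is illustrative, because the documents give no event rates. Take n = 150 per arm (Section 9.2), two-sided 5%, and assume the event risk doubles from p₁ to p₂ = 2p₁. With p̄ the mean of the two risks:

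power = Φ{ [ |p₂ − p₁| − 1.96·√(2p̄(1 − p̄)/n) ] / √(p₁(1 − p₁)/n + p₂(1 − p₂)/n) }

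| Assumed control risk | Doubled risk | Power |
|---|---|---|
| 2% | 4% | 0.17 |
| 5% | 10% | 0.38 |
| 10% | 20% | 0.68 |
| 20% | 40% | 0.97 |

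For the 5% row: [0.05 − 1.96 × 0.0304] / 0.0303 = −0.32, and Φ(−0.32) ≈ 0.38. For uncommon events, a comparison by arm would usually miss a doubling of risk. It complements individual assessment but does not replace it.

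**The case against.** The strongest defence is that the sentence describes serious events related to surgery or intensive care, with the event names in parentheses as examples. On that reading attribution comes first, and a drug-related shock lies outside the rule. The reading is possible, but it does not remove the defect. The text names shock, infection and organ failure as surgical or intensive-care events, assigns nobody to make the attribution, and applies to a population in which surgery is always an available explanation.

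Several stronger inferences are tempting, and the documents do not support them:

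- **That 8.4.2 flatly contradicts 8.4.** For haemodynamic change the two can be read together. For deaths, the wording of 8.4 makes cause irrelevant, so a careful reader would notify at once. What is missing is a stated precedence.
- **That detection of safety signals is blocked.** Recording continues under 6.2.4, and the infection endpoints are compared by arm. What is lost is individual relatedness assessment and SUSAR handling.
- **That treating infection as an outcome conflicts with exempting it from immediate notification.** It does not, since it is captured as an endpoint. Only the advance ruling on relatedness sits badly with a plan that expects the drug to affect the pneumonia rate (Section 2.3.1).
- **That serious bowel events would go unreported.** "Gastrointestinal perforation" and mesenteric ischaemia are on the immediate list and are notified once identified. The documents do not discuss how they may first present.
- **That centres would classify events differently.** The supplied text does not state the number of centres.

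A further objection stands as a caveat. The numbering runs from 8.1 to 8.4 and then to 8.4.2, and the abbreviation list includes the DSUR, which appears nowhere else in the supplied text. Causality or periodic-reporting text may exist in sections not seen.

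**Conclusion.** The point holds in limited form. Section 8.4.2 presets causality for eight event classes under a heading about timing. Applied literally, it takes those events out of individual relatedness assessment and SUSAR handling. The effect is greatest for shock, myocardial infarction, ventricular arrhythmia and organ failure, for which the supplied plan offers neither a dedicated endpoint nor a described comparison by arm. The overlap with 8.4 is clear for deaths and arguable for haemodynamic change.

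The number of events affected cannot be estimated from the documents, and the primary efficacy analysis is untouched. The conclusion rests on the sentence as printed, so it does not require that a causality procedure be absent elsewhere. If one exists in the unseen sections, it would itself conflict with this sentence and need reconciling. The change should be made because it concerns patient safety and costs little.

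**What to change.** Reconcile 8.4 and 8.4.2 as follows:

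1. Limit 8.4.2 to an exemption from immediate notification.
2. Replace the causality clause with a requirement that the blinded investigator assess relatedness for each serious event, and record it in the eCRF. Section 6.1 already blinds physicians to allocation.
3. State that 8.4 prevails whenever an event meets both sections.
4. Tabulate the exempted serious events by arm in the final report, over all randomised patients, so that early deaths left out of the mITT population are counted.
5. Check the new wording against any causality or reporting text in the sections not supplied.

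The cost is a protocol wording change, at most one eCRF field per serious event if none exists, one additional table, and slightly more investigator time per event. No treatment or clinical management rule is affected.

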9. STATISTICS

9.1. Statistical Methods

The analysis will proceed in 3 stages:

Descriptive Analysis:

Description of the total population and by group. For categorical variables: absolute and relative frequencies. For normally distributed continuous variables: mean and standard deviation. For non-normal distributions: median and interquartile range.

Inferential Analysis:

Comparisons between the 2 randomized groups will use chi-squared test for categorical variables; Student's t-test for Gaussian continuous variables; Wilcoxon-Mann-Whitney test for non-Gaussian variables. For pain scores over time, a mixed model for repeated measures will be used.

Exploratory Analysis:

Bivariate (correlation coefficients) or multivariate tests (multiple regression, logistic regression) to determine relationships between variables, including the effect of age, sex, and obesity (BMI>30).

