2. SCIENTIFIC JUSTIFICATION AND GENERAL DESCRIPTION

2.1. Study Context

Digestive complications following cardiac surgery are frequent and worsen patient prognosis. Paralytic ileus and Ogilvie syndrome are among these complications. They represent a real management challenge in intensive care, inducing morbidity-mortality, extended hospital stays, and significant postoperative costs. Few treatments appear effective for bowel transit recovery other than neostigmine, which has non-negligible side effects, particularly cardiac.

After cardiac surgery, opioid analgesics are frequently used to relieve pain, particularly sternotomy pain. Through their pharmacological effect, they contribute to postoperative paralytic ileus. Opioid receptors are distributed throughout the central nervous system, where they are involved in pain perception, but also peripherally, including in the mesenteric nervous system where they regulate peristalsis. Opioid receptor antagonists are therefore a prime target.

Naloxegol is a peripherally acting opioid receptor antagonist in tablet form, from the alvimopan family. It was designed to antagonize peripheral, but not central, effects of opioids at therapeutic doses. It is a substrate of cytochrome P450 and CYP3A4, rapidly absorbed with a mean time to maximum plasma concentration of 2 hours. Following once-daily administration, steady-state plasma concentrations are reached within 2-3 days with minimal accumulation. The main elimination route is hepatic, with minimal renal excretion.

Research hypothesis: Adding naloxegol pre- and postoperatively in cardiac surgery could reduce the time to bowel transit recovery and the rate of digestive and respiratory complications, as well as the duration of intensive care stay, without negative effects on analgesia.

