4.2. Secondary Endpoints

Related to Secondary Objective 1 – Digestive Complications Rate:

- Intra-abdominal pressure measured via an adapted urinary catheter on Day 1 and Day 2 minimum, until measurement is feasible (cmH₂O)
- Vomiting
- Ogilvie syndrome defined by an occlusive syndrome >72h and cecal distension >8cm
- Mesenteric ischemia documented via abdominal imaging, colonoscopy, or laparoscopy
- Need for colonoscopy
- Placement of nasogastric tube
- Intolerance to solid food at Day 2

Related to Secondary Objective 2 – Respiratory Complications Rate:

- Duration (hours) of invasive and non-invasive mechanical ventilation (NIV, Optiflow)
- Reintubation
- Assisted ventilation (invasive or non-invasive) at Day 2
- Pneumonia, defined by a radiological infiltrate plus at least 2 criteria: T>38°C; leukocytosis or leukopenia; purulent secretions

Related to Secondary Objective 3 – Infectious Complications Rate:

- Septicemia defined by two positive blood cultures with the same organism within 48h (catheter or peripheral)
- Superficial or deep sternal infection (return to operating room for wound)

Related to Secondary Objective 4 – Pain Assessment:

- VAS (Visual Analog Scale) at Day 1, Day 2, and Day 3
- Total opioid consumption in morphine equivalent mg

Related to Secondary Objective 5:

- Total hospitalization duration in days

Related to Secondary Objective 6:

- Length of stay in intensive care unit and CCU in days

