9.3. Significance Level

Bilateral threshold: 0.05

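### The 17 secondary endpoints are compared inferentially at an unadjusted two-sided 0.05, with no hierarchy or exploratory label in the visible text, so a false secondary benefit is several times more likely than the nominal 2.5%

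*Combined protocol and SAP*

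**What the plan says.** Section 4.1 names one primary endpoint, the time to first significant stool. Section 4.2 then groups the secondary endpoints by objective. Under "Related to Secondary Objective 1 – Digestive Complications Rate" there are seven items; under "Related to Secondary Objective 2 – Respiratory Complications Rate" four; under "Related to Secondary Objective 3 – Infectious Complications Rate" two. Pain has two items, and hospital stay and ICU/CCU stay have one each.

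Section 9.1 has descriptive, inferential and exploratory stages. The inferential stage reads: "Comparisons between the 2 randomized groups will use chi-squared test for categorical variables; Student's t-test for Gaussian continuous variables; Wilcoxon-Mann-Whitney test for non-Gaussian variables". It adds: "For pain scores over time, a mixed model for repeated measures will be used". The exploratory stage covers something else: "Bivariate (correlation coefficients) or multivariate tests (multiple regression, logistic regression) to determine relationships between variables". Section 9.3 consists of "Bilateral threshold: 0.05".

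The research hypothesis in section 2.1 is that naloxegol "could reduce the time to bowel transit recovery and the rate of digestive and respiratory complications, as well as the duration of intensive care stay".

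**The concern.** By the plan's own layout, the secondary comparisons between randomized groups are inferential, and the exploratory label goes to correlations and regressions. One threshold is given. Nothing visible makes secondary claims depend on the primary result, orders them, or divides alpha among them.

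Two features make this more than a formality. Section 2.1 hypothesises benefit on digestive complications, respiratory complications and intensive care stay, so these are results the trial is likely to be read for. And the digestive and respiratory objectives have no deciding variable. Each so-called rate is a list of separate items, including a continuous pressure in one list and a duration in the other. The plan does not say whether one, several or all items must differ.

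At stake is what may be concluded from an isolated secondary p<0.05, above all if the primary result is negative.

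**Working it through.** The plan gives no family-wise error rate, so there is no stated figure to reproduce. The only error rate that bears on this is the 0.05 in section 9.3.

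**Step 1. Count the tests (section 4.2).** 7 + 4 + 2 + 2 + 1 + 1 = 17, taking the pain scores on Days 1 to 3 as one test because section 9.1 uses one repeated-measures model. Splitting invasive from non-invasive ventilation and ICU from CCU stay would give 19.

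**Step 2. Define the families.**
- All secondary endpoints: m = 17.
- Items behind the section 2.1 benefit hypotheses (digestive, respiratory, ICU/CCU stay): 7 + 4 + 1 = 12.
- Digestive objective alone: m = 7.

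**Step 3. Formula.** Assume no true effect on any secondary endpoint. A two-sided 0.05 test gives a false result favouring naloxegol with probability 0.025. For m independent tests the chance of at least one is 1 − 0.975^m:
- m = 17: 1 − 0.975^17 = 0.350
- m = 12: 1 − 0.975^12 = 0.262
- m = 7: 1 − 0.975^7 = 0.162

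In either direction, for comparison: 1 − 0.95^17 = 0.582 and 1 − 0.95^7 = 0.302.

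**Step 4. Allow for correlation.** The documents give no correlations, so a common value ρ is assumed. Write each test statistic as √ρ·U + √(1−ρ)·E, with U shared, E specific to the test, and both standard normal. The chance of at least one false result favouring naloxegol is 1 − mean over U of Φ((1.96 − √ρ·U)/√(1−ρ))^m.

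| Family | m | ρ = 0 | ρ = 0.5 | ρ = 0.8 |
|---|---|---|---|---|
| All secondary, favouring naloxegol | 17 | 35% | 19% | 11% |
| Section 2.1 benefit items, favouring naloxegol | 12 | 26% | 16% | 9% |
| Digestive items, favouring naloxegol | 7 | 16% | 11% | 7% |
| All secondary, either direction | 17 | 58% | 39% | 21% |
| Digestive items, either direction | 7 | 30% | 23% | 15% |

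The nominal rate is 2.5% for the first three rows and 5% for the last two.

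**Step 5. Allow for rare events.** A chi-squared test on a rare event rarely reaches significance. At 150 per arm its exact two-sided size is 0.007 for an assumed event rate of 0.5%, 0.029 at 1% and 0.046 at 2%. The documents give no event rates. If six of the 17 items contributed nothing (an assumption), the 11 left would give 24%, 15% and 9% favouring naloxegol at ρ = 0, 0.5 and 0.8. The table therefore shows upper figures if items such as Ogilvie syndrome and mesenteric ischemia are rare, but the excess over 2.5% remains.

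**The case against.** The plan already sets the primary endpoint apart. Section 2.2 commits the trial to demonstrating an effect only on ileus duration. Section 3.2 uses softer verbs for the secondary objectives, and section 9.2 ties alpha and power to the primary endpoint alone. Nowhere does the plan say that one secondary p<0.05 meets an objective. Unadjusted secondary results beside a single primary are common. The analgesia items check that pain control is maintained, and the infection items are not part of the section 2.1 benefit hypothesis, so 17 overstates the number of benefit tests. Sections 9.4 to 9.6 are not visible and might contain a rule.

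Much of this stands. It is why the 12-item family is shown beside the 17, and why the point is confined to the visible text. If an unseen section holds a multiplicity rule, the sponsor need only point to it. What does not follow is that the softer verbs do the work of a label: section 9.1 has an exploratory category and does not put these comparisons in it.

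A reader might infer that a false claim of benefit is more likely than not. The figures do not support that. The 58% counts results in either direction, false harm included, and requires 17 independent tests; in naloxegol's favour the most is 35%. Independence is implausible too, since ventilation, reintubation, pneumonia and length of stay overlap. A reader might also infer that the primary conclusion is compromised. It is not: there is one primary endpoint, and its test needs no adjustment for the secondary ones.

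**Conclusion.** The point holds as a gap in how secondary results may be interpreted. With no true secondary effects, the chance of at least one false result favouring naloxegol is roughly four to eight times the nominal 2.5% at an assumed correlation of 0.5: 11% for the digestive items, 16% for the section 2.1 benefit items, 19% for all 17. Over correlations from 0.8 to 0 the corresponding ranges are 7% to 16%, 9% to 26% and 11% to 35%.

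These figures rest on every secondary null being true, on an assumed common correlation, and on each test having its full nominal size. The last makes them upper figures if some events are rare. The direction of the finding depends on none of the particular values. The matter should be settled before unblinding, but it does not threaten the primary analysis or the sample size.

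**What to change.** In sections 9.1 and 9.3, before unblinding, state that the primary endpoint is the only confirmatory test, at two-sided 0.05, and that all section 4.2 endpoints are exploratory, reported as estimates with 95% confidence intervals and with no claim of demonstrated benefit.

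If the sponsor wants confirmatory secondary claims, it should name one variable for each benefit in section 2.1 (digestive, respiratory, intensive care stay). The choice of variable is the sponsor's; the documents give no basis for ranking one item above another. Test these only if the primary is significant, by Holm at an overall two-sided 0.05. With three variables the smallest p-value is then compared with 0.05/3 = 0.0167. Everything else in section 4.2 stays exploratory.

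The cost is wording: no new data, no more patients, no change to the primary test. The downside is that an isolated secondary p<0.05 can no longer be reported as a demonstrated benefit.

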4. JUDGMENT CRITERIA

4.1. Primary Endpoint

Time (in hours) to bowel transit recovery after cardiac surgery, defined as the duration in hours between the first anesthetic induction and the emission of the first significant stool (approximately 100g as judged by the nursing assistant or nurse in charge of the patient, blinded to treatment).

The number of patients who received macrogol and the number who received picosulfate will be indicated for each arm.

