9.2. Sample Size Calculation

Primary endpoint: time to bowel transit recovery (quantitative variable). Calculation based on a mean transit recovery time of 48 hours postoperatively. For a 15% reduction (48h to 41h) in the treated group, standard deviation of 20h, alpha risk of 5%, power of 80%, bilateral test: 300 inclusions needed (150 patients per group).

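### Cheap improvement, not an error: the primary treatment effect could be prespecified with adjustment for age, sex and BMI, which the plan uses only in an exploratory regression.

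*Combined protocol and SAP*

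**What the plan says.** The primary endpoint (section 4.1) is "Time (in hours) to bowel transit recovery after cardiac surgery", counted from anaesthetic induction to the first significant stool. Section 9.2 treats it as continuous: "Primary endpoint: time to bowel transit recovery (quantitative variable".

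Under Inferential Analysis, section 9.1 says "Comparisons between the 2 randomized groups will use chi-squared test for categorical variables". For continuous variables it names a t-test or a Wilcoxon-Mann-Whitney test, depending on distribution. The only model there is the mixed model for repeated pain scores. The primary comparison is therefore an unadjusted two-sample test.

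Under Exploratory Analysis, the same section plans correlations and multiple or logistic regression, "including the effect of age, sex, and obesity (BMI>30". It does not say that treatment arm is in those models or that the primary endpoint is the outcome.

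Sections 6.2.1 and 6.7.3 describe 1:1 allocation in a sequential prepared order. No stratification is described, and no section plans an adjusted primary estimate.

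**The concern.** In a randomised comparison of a continuous outcome, adjusting for baseline factors that predict the outcome removes the variance they explain and narrows the confidence interval. This plan already intends to use age, sex and obesity, so it must record them, yet it keeps them out of the one comparison where they might sharpen the result.

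At stake is some efficiency, and the standing of any adjusted estimate reported later. If the adjusted effect first appears in a loosely described exploratory regression, readers can object that the model was chosen after the data were seen. Naming it in advance removes that objection.

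**Working it through.** **Inputs (section 9.2).** Control mean: "Calculation based on a mean transit recovery time of 48 hours postoperatively". Effect: "For a 15% reduction (48h to 41h) in the treated group", so 7 h. Spread: "standard deviation of 20h". Error rates: "alpha risk of 5%, power of 80%, bilateral test". Planned size: 150 per group, 300 in total.

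**The plan's own figure.** Normal approximation: n per group = 2 × (1.960 + 0.842)² × 20² / 7² = 128.1, so 129 per group and 258 in total. The plan states 300, so its figure does not follow from these inputs alone. That is a separate matter. Here it means only that 150 per group exceeds the stated power target.

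**Unadjusted power.** Standardised effect 7/20 = 0.35. A two-sided t-test at 5% with 150 per group has power 85.6% (85.8% by the normal approximation). The standard error is 20 × √(2/150) = 2.309 h and the 95% half-width is 1.96 × 2.309 = 4.53 h.

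**Adjusted power.** If the covariates explain a share R² of the outcome variance, the residual variance is 20² × (1 − R²). Estimating three covariate slopes with 295 residual degrees of freedom inflates the variance of the treatment estimate by about 1 + 3/295 = 1.010. The effective SD is then 20 × √[(1 − R²) × 1.010]. The documents give no R², so the range below is an assumption, and it starts at zero.

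| Assumed R² | Variance relative to unadjusted | Effective SD (h) | Power, 150 per arm |
|---|---|---|---|
| 0 | 1.010 | 20.10 | 85.2% |
| 0.02 | 0.990 | 19.90 | 85.9% |
| 0.05 | 0.960 | 19.59 | 87.0% |
| 0.10 | 0.909 | 19.07 | 88.7% |
| 0.20 | 0.808 | 17.98 | 91.9% |

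**Break-even.** Adjustment pays once (1 − R²) × 1.010 falls below 1, which is at R² of about 0.01. At R² = 0 the loss is 85.57% − 85.22% = 0.35 of a point.

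**Interval width.** At R² = 0.05, 0.10 and 0.20 the 95% half-width is about 4.43, 4.32 and 4.07 h, against 4.53 h unadjusted.

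**Simulation check.** 4,000 simulated trials per R², with three normally distributed covariates, gave unadjusted and adjusted power of 85.3% and 84.8% at R² = 0, 85.4% and 85.7% at 0.02, 85.8% and 87.4% at 0.05, 86.0% and 88.9% at 0.10, and 85.4% and 91.7% at 0.20. The Monte Carlo standard error is about √(0.85 × 0.15/4000) = 0.6 of a point, so this agrees with the table.

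All these figures are for a linear model. They are only approximate if the analysis is on ranks or uses a proportional-odds model.

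**The case against.** The strongest reply is that nothing in the plan fails. A t or Wilcoxon test is valid under 1:1 randomisation, choosing it is a legitimate preference, and on the sponsor's own inputs the trial has about 86% power against a target of 80%. This stands. It limits the point to an optional improvement. The surplus power does hold only if 7 h and 20 h are right, and section 9.2 gives no source for either.

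A reader might infer more than the documents support:

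- *That precision is certainly being lost.* The documents do not say how strongly age, sex or BMI predict time to first stool. At R² below about 0.01 there is nothing to gain. The larger gains need 10% to 20% explained variance from three general factors, for which the documents offer no evidence.
- *That the sponsor regards these factors as predictors of the primary endpoint.* Section 9.1 speaks only of relations between variables and does not name that endpoint.
- *That cutting BMI at 30 discards information from the primary analysis.* The cut belongs to the exploratory step. It matters here only because, if BMI is brought into the primary model, the continuous value should be used.
- *That the lack of described stratification is a further reason to adjust.* In a linear model, correcting chance imbalance and removing explained variance are largely one mechanism and should not be counted twice.

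Two practical objections also stand. The documents contain no list of baseline variables. Recording of the three factors is implied by the exploratory plan, and recording of BMI as a number is likely but not stated. And a Wilcoxon test has no place for covariates, so a fix that names only a linear model would leave that branch open.

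**Conclusion.** The point holds as a low-cost improvement and not as an error. The primary comparison in section 9.1 is unadjusted, and no adjusted primary estimate is planned although the needed factors appear elsewhere in the same section. Over an assumed R² of 0 to 0.20, prespecified adjustment moves power from 85.6% to somewhere between 85.2% and 91.9%. The possible loss is about a third of a point; the possible gain is about 6 points and may be negligible. This rests on the plan's 7 h and 20 h, on 150 analysed patients per arm, on a linear model with three covariates, and on R² values that are assumptions. The possible loss is small enough to make adjustment worth adopting, but the documents do not show that the present plan gives up a meaningful amount of precision.

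**What to change.** State in section 9.1, fixed before unblinding, that the primary treatment effect is estimated with adjustment for age, sex and BMI, with age and BMI continuous:

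- If times are treated as Gaussian: a linear model of time to transit recovery on arm, age, sex and BMI.
- If the Wilcoxon branch applies: a named adjusted counterpart, for example the same linear model on rank-transformed times, or a proportional-odds model. If proportional odds is chosen, say that the adjusted odds ratio is conditional on the covariates and is not the same quantity as the unadjusted one.
- Keep the unadjusted t or Wilcoxon test as a sensitivity analysis.
- Add a short rule for a missing covariate, and confirm that the eCRF holds BMI, or height and weight, and not only an obesity flag.

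The cost is a few sentences of specification and at most about 0.35 of a power point. No extra patients or visits are needed and, if BMI is recorded as a number, no new data.

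The obesity category can stay as it is in the exploratory analysis.
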